## Results

The most relevant results that can be concluded from this study are:

	Investigational product	Comparator product placebo
Skin depigmenting	The product showed a skin depigmenting effect after 84 days of products' intake, in comparison to the baseline. After 28 and 56 days of products' intake, no improvement was observed.	No improvement in the skin depigmenting was observed after 28, 56 and 84 days of products' intake, in comparison to the baseline.
	The investigational product has no effect on the skin depigmenting, in comparison to the placebo.	
	
 
– 28.00%, 52.08% and 61.22% of the subjects agreed to strongly agreed that their skin is with less hyperpigmentation spots 28, 56 and 84 days after the daily intake of the investigational product, respectively.
 
– 26.53%, 55.10% and 53.07% of the subjects agreed to strongly agreed that their skin is with less hyperpigmentation spots 28, 56 and 84 days after the daily intake of the placebo, respectively.
 
	
Skin whitening/brightening	The product demonstrated a skin whitening/lightening effect after 56 and 84 days of products' intake, in comparison to the baseline. After 28 days of products' intake, no improvement was observed.	The product demonstrated a skin whitening/lightening effect after 56 and 84 days of products' intake. After 28 days of products' intake, no improvement was observed.
	The investigational product has a skin whitening/brightening effect, in comparison to the placebo, after 84 days of products' intake.	
	
 
– 32.00%, 60.42% and 55.10% of the subjects agreed to strongly agreed that their skin had a luminous effect 28, 56 and 84 days after the daily intake of the investigational product, respectively.
 
– 32.65%, 51.02% and 57.14% of the subjects agreed to strongly agreed that their skin had a luminous effect 28, 56 and 84 days after the daily intake of the placebo, respectively.
 
	
Skin colour	The product revealed a skin tone lightening effect after 28, 56 and 84 consecutive days of products' intake, in comparison to the baseline.	The product revealed a skin tone lightening effect after 56 days of products' intake, in comparison to the baseline. After 28 and 84 days of products' intake, no improvement was observed.
	The investigational product has an almost statistically significant improvement in the skin tone lightening, in comparison to the placebo, after 84 days of products' intake, supporting the skin whitening/lightening effect observed previously.	
Skin tone evenness	No improvement in the skin tone evenness was observed after 28, 56 and 84 days of products' intake.	No improvement in the skin tone evenness was observed after 28, 56 and 84 days of products' intake.
	The investigational product has no effect on the skin tone evenness, in comparison to the placebo.	
	
 
– 32.00%, 60.42% and 67.34% of the subjects agreed to strongly agreed that their skin is with more homogeneous skin tone 28, 56 and 84 days after the daily intake of the investigational product, respectively.
 
– 32.65%, 59.18% and 59.18% of the subjects agreed to strongly agreed that their skin is with more homogeneous skin tone 28, 56 and 84 days after the daily intake of the placebo, respectively.
 
	
Skin density	No improvement in the density of the dermis was observed after 28, 56 and 84 days of products' intake.	No improvement in the density of the dermis was observed after 28, 56 and 84 days of products' intake.

	
intake, in comparison to the baseline. Instead, a significant decrease was observed.
 
The investigational product has no effect on the density of the dermis, in comparison to the placebo.
 
 
– 14.00%, 33.33% and 32.65% of the subjects agreed to strongly agreed that their skin is denser 28, 56 and 84 days after the daily intake of the investigational product, respectively.
 
– 22.45%, 36.73% and 38.77% of the subjects agreed to strongly agreed that their skin is denser 28, 56 and 84 days after the daily intake of the placebo, respectively.
 
	
intake, in comparison to the baseline. Instead, a significant decrease was observed.

Skin hydration	
No improvement in the skin hydration was observed after 28, 56 and 84 days of products' intake, in comparison to the baseline.
	
No improvement in the skin hydration was observed after 28, 56 and 84 days of products' intake, in comparison to the baseline. Instead, a decrease was observed after 84 days of products' intake.

	
The investigational product has no effect on the skin hydration, in comparison to the placebo.
	
	
 
– 50.00%, 60.42% and 61.23% and 36.73% of the subjects agreed to strongly agreed that their skin is more hydrated 28, 56 and 84 days after the daily intake of the investigational product, respectively.
 
– 36.73%, 51.02% and 69.39% of the subjects agreed to strongly agreed that their skin is more hydrated 28, 56 and 84 days after the daily intake of the Placebo, respectively.
 
	
	
No improvement in skin total deformation was observed after 28, 56 and 84 days of products' intake, in comparison to the baseline. Instead, an increase was observed after 84 days of products' intake.
	
No improvement in skin total deformation was observed after 28, 56 and 84 days of products' intake, in comparison to the baseline. Instead, an increase was observed after 84 days of products' intake.

Skin overall elasticity	
The investigational product has no effect on the skin total deformation, in comparison to the placebo.
	
	
No improvement in skin overall elasticity was observed after 28, 56 and 84 days of products' intake, in comparison to the baseline.
	
The product showed to increase the skin overall elasticity after 84 days of products' intake, in comparison to the baseline. After 28 and 56 consecutive days of products' intake, no improvement was observed.

	
The investigational product has no effect on skin overall elasticity, in comparison to the placebo.
	
Skin firmness	
No improvement in skin firmness was observed after 28, 56 and 84 days of products' intake, in comparison to the baseline.
	
The product showed to increase the skin firmness after 84 days of products' intake, in comparison to the baseline. After 28 and 56 consecutive days of products' intake, no improvement was observed.

	
The investigational product has no effect on skin firmness, in comparison to the placebo.)
	
	
 
– 18.00%, 37.50% and 42.86% of the subjects agreed to strongly agreed that their skin is firmer 28, 56 and 84 days after the daily intake of the investigational product, respectively.
 
– 28.57%, 40.81% and 42.85% of the subjects agreed to strongly agreed that their skin is firmer 28, 56 and 84 days after the daily intake of the placebo, respectively.
 
	
Skin radiance	
The product demonstrated a skin radiance effect after 28, 56 and 84 days of products' intake, in comparison to the baseline.
	
The product demonstrated a skin radiance effect after 28, 56 and 84 days of products' intake, in comparison to the baseline.

	The investigational product has no effect on the radiance condition of the subject's skin, in comparison to the placebo.
--	--

Additionally, the following results were obtained from the subjects' subjective evaluation:

- In a general way, 73.47% and 63.26% of the subjects evaluated the investigational product and placebo as good to very good, respectively, after 84 days of daily intake;
- 92% and 91.84% of the subjects agreed to strongly agreed that it was practical to include the investigational product and placebo in their daily routine, respectively;
- 75.51% and 67.35% of the subjects agreed to strongly agreed that their skin is with better appearance 84 days after the daily intake of the investigational product and placebo, respectively;
- 89.80% and 75.51% of the subjects agreed to strongly agreed that they would like to continue taking the supplement and placebo, respectively;
- 89.80% and 77.56% of the subjects agreed to strongly agreed that they would recommend the supplement and placebo to a friend, respectively.

The product was in general well tolerated by the subjects with no subjects reporting any serious adverse events. However, five subjects reported mild discomforts, which were resolved during the study.

The benefits of the investigation superposed the risks, as the efficacy degree of the products was assessed and no adverse events were observed.

The principal hypothesis of this clinical study is that the melanin variation parameters will decrease at least 7.02% after 28 days of the intake of the investigational product, compared to the placebo. This hypothesis was not verified with this clinical investigation.

In conclusion, the investigational product showed to have a skin whitening/brightening effect, in comparison to the placebo, after 84 days of products' intake, while no effects were observed for the skin depigmenting, skin tone evenness, skin density, skin hydration, skin total deformation, skin overall elasticity, skin firmness and skin radiance, in comparison to the placebo, after 28, 56 and 84 consecutive days of products' intake.

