### Study Protocol

The primary aim of this *in vivo* clinical study is to evaluate the depigmenting effect of an active ingredient incorporated into a food supplement through the evaluation of the melanin variation parameter, assessed with the equipment Antera 3D (Miravex, Ireland), after 28 consecutive days of food supplement's once-daily intake, in comparison with the baseline and a placebo.

The secondary objective of this study is to evaluate *in vivo* the depigmenting effect of the same active ingredient incorporated into a food supplement through the evaluation of the melanin variation parameter, assessed with the equipment Antera 3D (Miravex, Ireland), after 56 and 84 consecutive days of food supplement's once-daily intake.

Other goals of this clinical study are to evaluate *in vivo* the effect of the same active ingredient incorporated into a food supplement, after 28, 56 and 84 consecutive days of a once-daily intake, in comparison with the baseline and a placebo (1) on skin whitening/brightening through the evaluation of the L\* parameter, assessed with the equipment Antera 3D (Miravex, Ireland), (2) on the skin colour homogeneity through the measurement of the ITA° (Individual Typology Angle) parameter, assessed with the equipment Colorimeter® CL400, (3) on the skin tone evenness through the measurement of the standard deviation of the skin colour, assessed with the equipment Colorimeter® CL400, (4) on the skin density of the dermis, measured with the equipment Episcan 20 MHz (Longport Inc, United States), (5) on skin hydration assessed through capacitance measurements with the equipment Corneometer® CM825, (6) on the skin firmness, skin overall elasticity and skin total deformation measured with the equipment Cutometer® SEM 575 (Courage+Khazaka electronic GmbH, Germany), and (7) on skin radiance through clinical evaluation performed by an expert.

It is also objective of this clinical study to evaluate (8) subjects' tolerance, acceptability, perception of efficacy and future use/purchase intention towards the food supplements by filling out a subjective evaluation questionnaire after 28, 56 and 84 consecutive days of food supplement's once-daily intake.

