### **Statistical Analysis Plan**

A descriptive statistical analysis of the skin depigmenting, skin whitening/brightening, skin density, skin hydration, skin firmness, skin overall elasticity, skin total deformation and skin radiance results are performed for each group at each evaluation time-point, including the calculation of mean, standard deviation, and graphic representations.

Normality tests (Shapiro-Wilk test) are performed in order to assure normal distribution of the objective data obtained.

If normal distribution of the data is verified:

- paired-sample t-tests are applied to compare the results obtained for each parameter before (t0) versus after 28 (t1), 56 (t2) and 84 (t3) days of each food supplement's intake;
- independent t-tests are applied to compare the differences to baseline obtained with the investigational product versus the ones obtained with the comparator product at each time-point of evaluation (t1, t2 and t3).

For non-normal distributions non-parametric tests are used:

- Wilcoxon-tests are applied to compare the results obtained for each parameter before (t0) versus after 28 (t1), 56 (t2) and 84 (t3) days of each food supplement's intake;
- Mann-Whitney tests are applied to compare the differences to baseline obtained with the investigational product versus the ones obtained with the comparator product at each time-point of evaluation (t1, t2 and t3).

The significance value is established at 0.05 and at a power of 0.95.

Descriptive statistics of the subjective evaluation is performed at each time-point of evaluation with the calculation of number and percentage of subjects responding to each answer option and the results presented in graphic representations.

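### The conclusion presents L* at day 84, the only reported positive among 30 planned unadjusted placebo comparisons, as a demonstrated effect with no exploratory label

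*Combined protocol and SAP*

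**What the plan says.** The Study Protocol makes melanin variation at day 28 the primary aim and melanin at days 56 and 84 the secondary objective. Everything else follows under "Other goals of this clinical study are to evaluate", and L* is item (1) of that list.

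For normally distributed data, the Statistical Analysis Plan states that "independent t-tests are applied to compare the differences to baseline obtained with the investigational product" with those on placebo at each of the three visits; Mann-Whitney tests replace them otherwise. On error control it says only "The significance value is established at 0.05 and at a power of 0.95". It gives no adjustment, no testing order and no sidedness.

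The L* row of the Results says "The investigational product has a skin whitening/brightening effect, in comparison to the placebo, after 84 days of products' intake". The skin-colour row says "The investigational product has an almost statistically significant improvement in the skin tone lightening, in comparison to the placebo" at day 84, and describes this as "supporting the skin whitening/lightening effect observed previously". Of the principal hypothesis (melanin at day 28 against placebo) the Results say "This hypothesis was not verified with this clinical investigation". The next sentence is the conclusion: "In conclusion, the investigational product showed to have a skin whitening/brightening effect, in comparison to the placebo, after 84 days of products' intake". It goes on to list eight parameters with no effect against placebo at any visit.

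**The concern.** This is the report's only affirmative efficacy claim against placebo, and it comes from a trial whose primary hypothesis failed. The claim rests on one low-ranked comparison out of many, each tested at the full 0.05. One favourable result in such a set is unremarkable even if the product does nothing. Yet neither the L* row nor the conclusion calls the finding exploratory, nominal or unadjusted, so a reader would take it as established.

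Two details add to this. A skin-colour result that missed the plan's own threshold is used to strengthen the L* claim. Skin colour is then the only one of the ten parameters missing from the conclusion.

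**Working it through.** The documents state neither a number of comparisons nor a familywise error rate, so there is no figure of the plan's own to reproduce. Both are derived here.

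**1. Count of placebo comparisons.** The Study Protocol names ten measured parameters: melanin, L*, ITA° (skin colour), SD of skin colour (tone evenness), dermis density, hydration, firmness, overall elasticity, total deformation and radiance. The Statistical Analysis Plan compares each with placebo at t1, t2 and t3: 10 × 3 = 30.

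**2. Reported status of the 30.**

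| Status | Comparisons | Number |
|---|---|---|
| Positive | L*, day 84 | 1 |
| Stated as no effect | 8 parameters × 3 visits | 24 |
| Missed 0.05 | Skin colour, day 84 | 1 |
| Not stated | L* and skin colour, days 28 and 56 | 4 |
| Total | | 30 |

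The primary comparison (melanin, day 28) is one of the 24 nulls. That leaves 29 non-primary comparisons.

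**3. Chance of at least one favourable p<0.05 among the 29 for an inert product.** Assuming two-sided tests, each has a 0.025 chance of a favourable false positive.

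- Expected number: 29 × 0.025 = 0.725. One is reported.
- Independent tests: 1 − 0.975^29 = 0.520.
- Correlated tests: 400,000 simulated sets of 10 × 3 normal test statistics with exchangeable correlation between visits and between parameters, melanin at day 28 excluded, favourable meaning z > 1.96. The documents give no correlations, so these are assumptions:

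| Between visits | Between parameters | Chance of at least one |
|---|---|---|
| 0.5 | 0.2 | 0.40 |
| 0.7 | 0.2 | 0.36 |
| 0.7 | 0.5 | 0.27 |
| 0.9 | 0.5 | 0.215 |
| 0.9 | 0.7 | 0.16 |

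**4. Sensitivity to the count and to sidedness.**

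- The plan's descriptive-statistics list names only eight parameters, without skin colour and tone evenness. That gives 8 × 3 − 1 = 23 non-primary tests: 1 − 0.975^23 = 0.441 if independent, and 0.19 at correlations 0.9 and 0.5.
- If the tests were one-sided at 0.05, the expected number would be 29 × 0.05 = 1.45. The chance would be 1 − 0.95^29 = 0.774 if independent, and 0.34 at 0.9 and 0.5.

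**5. What adjustment would have required.** Bonferroni over 29 tests needs p < 0.05/29 = 0.00172. The L* sample size is not given, so take 49 per arm from the day-84 questionnaire percentages (61.22% = 30/49 on product, 57.14% = 28/49 on placebo). With df = 96, the smallest significant difference is t × √(2/49):

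- unadjusted: 1.985 × 0.202 = 0.40 SD
- Bonferroni: 3.225 × 0.202 = 0.65 SD

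With 55 per arm (an equal split of the 110 enrolled, assumed), the figures are 0.38 and 0.61 SD. No L* p-value is given, so it is unknown whether the result would survive.

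**6. Other results bearing on L*.** Placebo also showed whitening against baseline at days 56 and 84. At day 84, 55.10% on product and 57.14% on placebo reported a luminous effect. Melanin showed no effect against placebo. None of this refutes L*, but it offers little corroboration.

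**The case against.** The strongest reply is that the context is already on the page. The failed primary hypothesis is stated in the sentence before, the conclusion itself lists eight null parameters, and the claim is confined to one parameter and one visit. This is true, and the problem is not concealment. But the disclosure does not tell a reader that L* was a low-ranked test made without adjustment, and the verb remains confirmatory.

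Second, skin colour and L* come from different instruments and point the same way at day 84. Calling them directionally consistent would be fair if the non-significance were stated plainly. However, both are related colour measures, so agreement is weak evidence, and a missed threshold does not support a claim. Omitting skin colour does not make the conclusion assert anything for it, but it leaves the list of results incomplete.

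Third, the Results present only the most relevant findings, so estimates and p-values may exist in a fuller report. Confining the L* and skin-colour results to day 84 also suggests that the earlier visits were not positive. Both points are reasonable. They are why the fix accepts a pointer to a full report and asks only that the four comparisons be stated.

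Fourth, the probabilities depend on assumed correlations and sidedness and on treating 29 tests as one family. This stands: 21% is not a floor, since correlations of 0.9 and 0.7 give 16%. Every setting examined is still well above 5%.

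**Conclusion.** The concern holds. L* at day 84 is the single reported positive among 30 planned unadjusted placebo comparisons, from the lowest tier of objectives, in a trial whose primary hypothesis was not verified, and it is stated as a demonstrated effect. For an inert product, the chance of at least one such favourable result among the 29 non-primary tests is about 21% to 52% (16% under the strongest correlation tried). This assumes two-sided testing, exchangeable correlations that the documents do not give, and the derived count; the narrower eight-parameter count gives 19% to 44%. If any of the four unstated comparisons were also positive, the chance explanation would be weaker. The finding is that the wording overstates the evidence, not that the L* effect is absent. Because it concerns the report's one positive claim against placebo, it must be corrected.

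**What to change.** - **L* row and conclusion:** describe L* at day 84 as an exploratory, nominal difference, one of 30 planned unadjusted placebo comparisons in a trial whose primary hypothesis was not verified, and needing confirmation. Give the between-group estimate, 95% CI and exact p-value, or point to them if a full report holds them.
- **Skin-colour row:** report day 84 as not significant at 0.05. Remove the near-significance wording and the statement that it supports L*. Add skin colour to the conclusion's list of results.
- **Unstated comparisons:** state the placebo comparisons for L* and skin colour at days 28 and 56.
- **Multiplicity:** do not add a testing sequence to the Statistical Analysis Plan now as if it had been pre-specified. Label any adjusted p-values as post hoc.

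The cost is three reworded sentences, four comparisons stated, and figures from data already collected. The downside for the sponsor is a weaker L* claim.

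### A skin-colour comparison with placebo that missed the 0.05 level is offered as support for the whitening claim, and the conclusion then leaves skin colour out

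*Combined protocol and SAP*

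**What the plan says.** The Study Protocol section gives three colour-related goals separate measures. Goal (1), whitening/brightening, is measured by L\* on the Antera 3D. Goal (2) is to study the effect "on the skin colour homogeneity through the measurement of the ITA" (that is, ITA°, on the colorimeter). Goal (3), tone evenness, is measured by the standard deviation of skin colour on the same colorimeter.

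The Statistical Analysis Plan compares changes from baseline between the two products at each visit, by independent t-test or Mann-Whitney test. On the threshold it says "The significance value is established at 0.05". It defines no category for results near that level.

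In the skin colour row of the Results table, the only statement against placebo is that at day 84 the investigational product "has an almost statistically significant improvement in the skin tone lightening, in comparison to the placebo". The same sentence goes on to describe this as "supporting the skin whitening/lightening effect observed previously".

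The last paragraph of the Results claims a whitening/brightening effect against placebo at day 84. For the remaining parameters it says "no effects were observed for the skin depigmenting, skin tone evenness, skin density", and continues with hydration, total deformation, overall elasticity, firmness and radiance. Skin colour appears in neither part.

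**The concern.** L\* at day 84 is the only measured parameter for which the document claims an advantage over placebo, and the Results state that the principal hypothesis, on melanin at day 28, was not verified. Whether a second endpoint corroborates L\* therefore matters to how the trial is read.

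The skin colour row appears to supply that corroboration, but by its own description the comparison did not meet the plan's criterion. The eight other parameters without a claimed advantage are written up as having no effect; this one is written up as an improvement. The conclusion, which is the part most likely to be quoted, then does not say where skin colour stands.

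The label adds to the problem. Read as homogeneity, as goal (2) has it, the parameter would not bear on whitening. Read as lightening, it looks like a second whitening endpoint.

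**Working it through.** The documents give no skin-colour estimate, standard deviation, interval or p-value against placebo, so there is no figure to reproduce. The check sets the sections side by side.

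**1. Status of the day-84 result.** The threshold is 0.05 (Statistical Analysis Plan). A result described as almost significant has not reached it. The plan does not say whether tests are one- or two-sided, but that does not alter this reading.

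**2. Accounting for the parameters compared with placebo.**

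| Parameter (Study Protocol) | Against placebo (Results table) | Closing conclusion |
|---|---|---|
| Melanin variation (depigmenting) | no effect | null list |
| L\* (whitening/brightening) | effect at day 84 | positive |
| Skin colour (inferred to be ITA°) | short of significance at day 84; days 28 and 56 not stated | absent |
| SD of skin colour (evenness) | no effect | null list |
| Dermal density | no effect | null list |
| Hydration | no effect | null list |
| Total deformation | no effect | null list |
| Overall elasticity | no effect | null list |
| Firmness | no effect | null list |
| Radiance | no effect | null list |

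Parameters compared: 10. Named in the conclusion: 1 positive + 8 null = 9. Unaccounted for: 10 − 9 = 1, which is skin colour.

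**3. Is the skin colour row ITA°?** The Results never print the name. Goal (2) uses the words skin colour, and melanin, L\* and evenness each have their own row, so ITA° is the only colour measure left. This is an inference. Steps 1 and 2 do not depend on it.

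**4. Label.** The objectives assign ITA° to homogeneity, while the row speaks only of lightening. The Statistical Analysis Plan does not settle the matter: its list of outcomes for descriptive analysis names neither skin colour nor tone evenness.

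**5. Do neighbouring results supply the corroboration instead?** They do not. Depigmenting showed no effect against placebo. The placebo arm also showed whitening against baseline at days 56 and 84, and skin tone lightening at day 56. Agreement that the skin looked luminous at day 84 was 55.10% on the investigational product and 57.14% on placebo.

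**The case against.** The strongest reply is that nothing is hidden. The skin colour row gives both arms against baseline at every visit, including the placebo arm's lightening at day 56, and says openly that significance against placebo was not reached at day 84. The conclusion neither counts skin colour as positive nor cites it in support of L\*. Moving it to the null list would leave the number of claimed advantages at one. A near-miss is also not evidence of no effect, so adding it unchanged to a list headed by that phrase would be a new error. All of this stands. It narrows the point to one clause in the table, one incomplete list and one inconsistent label.

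Three stronger readings may tempt a reader, and the documents do not support them.

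- *That ITA° was relabelled after the results were seen.* Nothing dates the lightening reading, and neither the parameter nor the instrument is shown to have changed. Because evenness has its own measure under goal (3), homogeneity may simply be a loose label for ITA° in the objectives.
- *That this is selective reporting.* The result is disclosed in the table. What is missing is its place in the conclusion, its statistics, and the comparisons with placebo at days 28 and 56.
- *That the size of the problem can be shown by counting all tests across parameters and visits and computing a false-positive chance.* That measures multiplicity, which is a separate issue and would be the same had skin colour been listed correctly. It would also need the unreported day-28 and day-56 results to be assumed.

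**Conclusion.** The point holds as a defect in how the results are worded and concluded. A comparison that missed the plan's 0.05 level should not be presented as support for another endpoint, and one of ten parameters compared with placebo is missing from the conclusion. Once the supporting clause is removed, the whitening claim rests on L\* at day 84 alone. The finding on the principal hypothesis is unaffected.

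Two assumptions carry this: that almost significant means the 0.05 level was not met, and, for the labelling part only, that the skin colour row is ITA°. The shortfall applies to the comparison with placebo; against baseline, the investigational arm is reported as improved at all three visits. Nothing can be said about the comparison with placebo at days 28 and 56, or about how large the day-84 difference was.

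**What to change.** - **Results table, skin colour row:** delete the near-significance and supporting wording. Give the between-group difference in change from baseline, with 95% CI and p-value, at days 28, 56 and 84. State that day 84 was not significant at 0.05.
- **Closing conclusion:** replace the no-effects phrase with *no statistically significant difference from placebo was shown*. Add skin colour (ITA°) at day 84, and at days 28 and 56 if those results confirm it.
- **Labels:** state that the skin colour row is ITA°, if that is so. Use one construct for it in the objectives and the results, and mark the lightening reading as exploratory unless it was specified in advance.

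The cost is wording plus statistics that the planned between-group analysis already produces; no new data are needed. The price to the sponsor is that the whitening claim loses its stated second support.
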